8.6 Treatment Exposure and Compliance

The duration of exposure (days) to a study drug, total amount of study drug administered and average daily dosage of study drug (per kg body weight) administrated will be summarized with descriptive statistics by underlying disease and treatment arm. For patients with conjugated bilirubin levels > 2 mg/dL, the cumulative dose administrated before the primary endpoint is reached (bilirubin >2 mg/dL) will be summarized by underlying disease and treatment arm.

Duration of exposure will be calculated as the difference between the date of last infusion of a study drug and the date of first infusion with a study drug plus 1 day. A data listing for treatment exposure will be included.

The duration, dose, and type of pre-treatment will be extracted from prior and concomitant medication form and summarized with descriptive statistics by underlying disease and treatment group. The frequency and percentage of patients who received PN for pre-treatment will be summarized by treatment group.

Compliance will be assessed by

- the ratio of the actual number of study drug infusions over the expected number of study drug infusions expressed as percent
- the ratio of the actual cumulative dose over the expected cumulative dose

evaluated separately over the initial and extension phase, resp., and summarized descriptively by treatment group and study phase.

Infusion of study drug will be expected on a given Study Day over the treatment period (Day 1 to Day 28 for initial treatment phase and Day 29 to Day 85 for treatment extension phase). Treatment with a study drug on a given Study Day will be considered an actual study drug infusion, provided any interruption of study drug infusion does not exceed 4 hours. Any interruption of the infusion of study drug longer than 4 hours will be documented and explained in the eCRF.

Compliance data will be provided in a data listing by patient.

Dose interruption (dose delay and modification) will be summarized with descriptive statistics (frequency and percentage) by treatment group.

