Study Day	Patients < 1500 g	Patients ≥ 1500 g
Day 1	1.0 g/kg/day	2.0 g/kg/day
Day 2	2.0 g/kg/day	3.0 g/kg/day
Day 3+	3.0 g/kg/day	3.0 g/kg/day

Investigational or control drug will be infused over 20 - 24 hours, as per hospital policy, at a weight based infusion rate. If the blood draw is from the PN/lipid infusion line, then lipid (study drug) should be held for 4 hours prior to the time of blood sampling. During study treatment, serum triglycerides (TGs) will be monitored to adjust lipid dose keeping TG levels < 250 mg/dL.

Blood samples for TG monitoring will be collected as follows:

Patients < 1500 g: At 1 g, 2 g and first dose of 3 g/kg/day

Patients ≥ 1500 g: At first dose of 3 g/kg/day

Once the target dose has been reached TGs will be assessed on a weekly basis.

Should TGs exceed 250 mg/dL, lipids will be paused until analysis of another blood sample on the following morning. If TGs are below 250 mg/dL lipids are restarted. If not this procedure has to be repeated the next morning.

Dosage of other PN components:

In addition to the study drug other macronutrients will be administered at a targeted dose as follows:

- Amino acids: 2 to 4 g/kg/day
- Dextrose: 8 to 18 mg/kg/min
- Trace elements, electrolytes, vitamins will be considered according to hospital practice and applicable guidelines.
- Use and dose of heparin and carnitine have to be documented in the concomitant mediation section in the CRF.

Route of Administration: The lipid emulsions will be infused into a central or peripheral vein

Treatment: Treatment group 1: Smoflipid 20% (investigational drug)

Clinical Study Protocol SMOF-018-CP3 Smoflipid 20% lipid injectable emulsion

Treatment group 2: Intralipid 20% (control drug)

Intravenous lipid dose management

Conjugated bilirubin levels in plasma will be assessed on a weekly basis during the initial treatment phase (visits Day 1 – Day 29) and then bi-weekly in the treatment extension phase (visits Day 36 - Day 85). If in the treatment extension phase conjugated bilirubin levels increase beyond 1.5 mg/dL, then conjugated bilirubin will be assessed weekly.

- **Lipid minimization:**

If at any point conjugated bilirubin exceeds 1.5 mg/dL (> 1.5 mg/dL), lipid dose has to be decreased to 1 g/kg/day immediately; dextrose dose should be increased accordingly to maintain adequate energy provision. Lipid dose will be maintained at 1 g/kg/d and not be increased again even if conjugated bilirubin levels decrease again below 1.5 mg/dL.

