- **Early discontinuation:**

Should conjugated bilirubin exceed 2 mg/dL (> 2 mg/dL), a confirmatory analysis must be performed after 7 days. The patient's dose will remain at 1 g/kg/day until analysis of the confirmatory blood sample. If the confirmatory analysis reveals that conjugated bilirubin increased further by at least 1 mg/dL, then the patient has to be removed from the study immediately and may be treated with an alternative lipid emulsion at the investigator's discretion. If not, the patient continues to receive study medication.

- **Weaning of lipids and PN:**

As soon as the patient receives 80 mL/kg/day oral/enteral feeding and achieved tolerance (i.e. at least 3 days) the dose of study drug must be reduced to 1 g/kg/d.

As soon as patient receives 100 mL/kg/day oral/enteral feeding and achieved tolerance (i.e. at least 3 days) study drug must be stopped completely.

Duration of Treatment:

The expected administration of lipid emulsions for each study patient should be 28 days. If PN is still indicated after 28 days, patients may receive the study drug for up to 84 days.

Patients:

Hospitalized neonates and infants, expected to require PN for 28 days

Clinical Study Protocol SMOF-018-CP3

Smoflipid 20% lipid injectable emulsion

Inclusion Criteria:

1. Neonates and infants, expected to require PN for 28 days
2. Postmenstrual age \geq 24 weeks
3. Birth weight \geq 750g
4. Gastrochisis, duodenal, jejunal or ileal atresia, volvulus, spontaneous intestinal perforation or necrotizing enterocolitis (Bell's stage 2B or higher)
5. At least 80% of nutritional needs at Baseline are met with PN
6. Signed and dated informed consent obtained from at least one parent or legal guardian

Exclusion Criteria:

1. Conjugated bilirubin > 0.6 mg/dL
2. Any known pre-, intra- or posthepatic complication that will increase conjugated bilirubin levels > 0.6 mg/dL during study participation
3. Suspected liver disease or liver damage based on either AST, ALT, or GGT exceeding 2.5x upper limit of normal range
4. Active bloodstream infection demonstrated by positive blood culture at screening
5. Cystic fibrosis
6. Meconium ileus
7. Serum TGs > 250 mg/dL
8. Cyanotic congenital heart defect
9. Severe renal failure as evidenced by creatinine > 2.0 mg/dL
10. History of shock requiring vasopressors
11. Anasarca
12. Extracorporeal Membrane Oxygenation (ECMO)
13. Known inborn errors of metabolism
14. Known congenital viral infection

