12.2.5 Day 29, Day 85, and End-of-Treatment Visit

The same procedures have to be performed on Day 29 (end of initial treatment phase), Day 85 (end of treatment extension phase), and the first day after receipt of the last dose of study medication (End-of-Treatment Visit), independent of the reason for which the study medication was stopped.

Conditions for continuing in the study after Day 29 / End-of-Treatment Visit:

Patients may continue in the study after the Day 29 / End-of-Treatment Visit if:

- PN is still indicated,
and/or
- Conjugated bilirubin $> 1.5 \text{ mg/dL}$

If the patient will continue to receive PN into the study extension phase (after Day 28) and later

Clinical Study Protocol SMOF-018-CP3

Smoflipid 20% lipid injectable emulsion

weaned from study medication with a conjugated bilirubin value ≤ 1.5 mg/dL, then the End-of-Treatment Visit must be performed on the first day after receipt of the last dose of study medication.

If the patient has been weaned from study medication with a conjugated bilirubin value > 1.5 mg/dL, the patient needs to complete the End-of-Treatment Visit on the first day after receipt of the last dose of study medication, but will continue to be followed up until conjugated bilirubin levels are ≤ 1.5 mg/dL. Conjugated bilirubin levels must be assessed weekly until they are ≤ 1.5 mg/dL. As the patient will receive no study medication after the End-of-Study Visit, no additional evaluations will be performed.

If consent is withdrawn, the parent(s) or guardian(s) of the patient should be encouraged to allow the patient to complete scheduled evaluations, including the End-of-Treatment Visit evaluations and the Follow-Up Visit, and informed that the patient will be given appropriate care under medical supervision until any ongoing AEs resolve or until the patient's condition becomes stable.

No patient will receive study medication beyond Day 84 of the study.

The following procedures will be performed

- Recording of physical examination and body measurements
 - physical inspection
 - body weight
 - body length measured by a length board
 - head circumference
- Recording of vital signs
 - blood pressure
 - heart rate
 - body temperature
- Collection of a blood sample for local laboratory analysis of the following parameters:
 - Biochemistry: total bilirubin, AST, ALT, GGT, ALP, TGs, Cr, glucose, CRP
 - Hematology: CBC, leukocytes, platelets, erythrocytes, hemoglobin, hematocrit
 - Coagulation: INR

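### SAP 8.6 expects an infusion on every calendar day to Day 28 and Day 85, so protocol-directed stops and triglyceride holds count as missed infusions and the extension ratio cannot exceed 98.2%

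*SAP*

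**What the plan says.** SAP 8.6 (Treatment Exposure and Compliance) gives two compliance measures, each evaluated separately for the initial and extension phases and summarized by treatment group:

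- an infusion count: "the ratio of the actual number of study drug infusions over the expected number of study drug infusions expressed as percent";
- a dose ratio: "the ratio of the actual cumulative dose over the expected cumulative dose".

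For the first, an infusion is expected on each study day of the treatment period, given as "Day 1 to Day 28 for initial treatment phase and Day 29 to Day 85 for treatment extension phase". A treated day counts as an actual infusion "provided any interruption of study drug infusion does not exceed 4 hours". For the second, the SAP does not define the expected cumulative dose.

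The protocol sets these limits on dosing:

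- **Last dosing day.** Section 12.2.5: "No patient will receive study medication beyond Day 84 of the study". The Study Outline (Duration of Treatment) agrees: "patients may receive the study drug for up to 84 days". In the study schedule, Day 85 is the End-of-Treatment visit, held the day after the last dose.
- **Weaning.** Once enteral or oral feeding of 100 mL/kg/day is tolerated, "study drug must be stopped completely" (Study Outline; also Section 11.3). This can happen on any study day.
- **Triglycerides above 250 mg/dL.** "lipids will be paused until analysis of another blood sample on the following morning", repeated daily if needed (Study Outline; also Section 11.3).
- **Conjugated bilirubin.** Above 1.5 mg/dL the lipid dose is cut to 1 g/kg/day. Above 2 mg/dL with a further rise of at least 1 mg/dL after 7 days, the infant is removed from the study (Study Outline; Section 10.4).

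**The concern.** A compliance ratio should show whether treatment was given as the protocol required. Here the denominator runs to a fixed calendar day, while the protocol tells sites to stop or hold study drug according to feeding tolerance and laboratory results. A site that follows those instructions loses compliance points.

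The events that reduce the ratio are themselves reported as study results: time to full feeds (SAP 8.11.2) and withdrawal for elevated conjugated bilirubin (SAP 8.12.2). If the arms differ on these, Table 14.3.5.2 will show a compliance difference even with equal adherence. An arm that weans sooner would look less compliant. In addition, the extension window contains one day on which the protocol permits no dose.

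**Working it through.** **1. Days expected under SAP 8.6** (last day − first day + 1)

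- Initial phase: 28 − 1 + 1 = 28.
- Extension: 85 − 29 + 1 = 57.
- Total: 28 + 57 = 85.

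**2. Days on which the protocol permits dosing**

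- Initial phase: 28, in agreement with the SAP.
- Extension: 84 − 29 + 1 = 56, one fewer than expected.
- Ceiling of the extension infusion ratio: 56/57 = 98.2%.

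**3. Protocol-directed stop, every earlier day dosed**

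| Last dose | Phase | Ratio as written |
|---|---|---|
| Day 14 | Initial | 14/28 = 50.0% |
| Day 20 | Initial | 20/28 = 71.4% |
| Day 24 | Initial | 24/28 = 85.7% |
| Day 35 | Extension | 7/57 = 12.3% |
| Day 42 | Extension | 14/57 = 24.6% |
| Day 56 | Extension | 28/57 = 49.1% |
| Day 70 | Extension | 42/57 = 73.7% |

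The arithmetic is the same whether the stop is weaning or bilirubin-directed removal. Fourteen days of study drug satisfies the duration requirement of the per protocol set (SAP 6.3), yet scores 50.0%.

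**4. Triglyceride hold.** A pause until the next morning's result will ordinarily exceed 4 hours, which removes the day from the numerator. One such day gives 27/28 = 96.4% in the initial phase and 55/57 = 96.5% in the extension (56 permitted days less one).

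**5. Bilirubin-triggered dose reduction.** The infant is still infused daily, so the infusion count does not change. Only the dose ratio can move, and only under an assumption about expected dose. Suppose it means the full target of 3 g/kg/day for 28 days, 3 × 28 = 84 g/kg, with reduction to 1 g/kg/day from Day 15:

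- Already at 3 g/kg/day on Day 1: (14 × 3 + 14 × 1)/84 = 56/84 = 66.7%.
- Ramp-up, 1500 g or more: (2 + 13 × 3 + 14 × 1)/84 = 55/84 = 65.5%.
- Ramp-up, below 1500 g: (1 + 2 + 12 × 3 + 14 × 1)/84 = 53/84 = 63.1%.

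On the same assumption, ramp-up with no reduction scores 83/84 = 98.8% or 81/84 = 96.4%. If expected dose instead means the dose the protocol required each day, all of these are 100%.

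**6. With the denominator tied to the protocol.** Last dose on Day 20 by weaning: 20/20 = 100%. Last dose on Day 42 by weaning: 14/14 = 100% in the extension. If the extension window ends at the protocol's Day 84 limit, full dosing scores 56/56 = 100%. Consent withdrawal after Day 20 stays at 20/28 = 71.4%, as it should.

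**The case against.** **The windows may only label the phases.** SAP 8.6 speaks of a treatment period, which could mean each infant's own, with the parenthesis merely marking the two phases. The extension is optional, which favours that reading. But the parenthesis gives calendar days, and nothing else in the SAP makes the period patient-specific. If the individual reading was meant, the same infant scores 14/14 or 14/57 depending on the programmer, and Day 85 and the triglyceride holds remain unsettled. The SAP also does not say whether infants who never enter the extension score 0/57 or are left out.

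**Little depends on it.** This stands. The per protocol set rests on at least 14 days of study drug and reviewed deviations, not on this ratio. The final analysis tests no hypotheses (SAP 4.5 and 7). The one-day mismatch costs 1/57 = 1.8 points and applies equally to both arms.

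**The information is available elsewhere.** This also stands. A reader might infer that the exposure table is compromised too. It is not: duration, total amount and average daily dose are reported in Table 14.3.5.1, and dose delay and interruption in Table 14.3.5.4. Neither uses this denominator. Weaning and bilirubin withdrawals have their own summaries.

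**Dose cuts and blood draws.** A reader might also infer that every bilirubin-triggered dose cut lowers compliance. It cannot lower the infusion count, and its effect on the dose ratio is undetermined while expected dose is undefined. Nor does the 4-hour hold before a blood draw count against a site if kept to 4 hours, since it does not exceed the limit.

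**Conclusion.** As written, the infusion-count denominator in SAP 8.6 scores correct conduct as missed infusions. The extension ratio cannot exceed 98.2%, and protocol-directed stops produce far lower values, such as 71.4% for a last dose on Day 20 and 24.6% for one on Day 42. These figures rest on reading the windows as the calendar days stated, with every day before the stop dosed.

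The loss is confined to the interpretability of one descriptive by-arm table. The documents do not show that the arms differ in weaning, holds or removal, so a misleading between-arm contrast is a possibility, not a finding. That 100% is unattainable is shown for the extension infusion count only. For the dose ratio the defect is an undefined term; the 63% to 67% range holds only if expected dose is taken as the full target dose throughout.

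The table should be corrected because the stated rule yields a figure that does not measure adherence, and the repair is cheap.

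**What to change.** Amend SAP 8.6 as follows:

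1. Reconcile the Day 85 limit of the extension window with the protocol's Day 84 limit on study drug.
2. Count expected infusions from first dose to the infant's protocol-directed stop: weaning, bilirubin-directed removal, or the end of the permitted period. Leave out days held under a protocol rule.
3. Do not shorten the count for consent withdrawal or other non-protocol stops. Ending it at any withdrawal would give 100% to an infant taken off treatment early and hide what a compliance measure should show.
4. Define expected cumulative dose as the sum of the doses the protocol required on each day.
5. Include only infants who entered the extension in the extension denominator.

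The cost is SAP wording and a revised derivation. Daily study drug dose and enteral and oral intake are already recorded (Protocol 12.2.3), and interruptions longer than 4 hours are already explained in the eCRF (Protocol 11.4). No new data are needed and no clinical rule changes.

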8.7 Subgroup Analysis

The primary endpoint (using the ITT analysis set and the per protocol set) as well as adverse events will be summarized by treatment group for the subgroups of ethnicity (Hispanic/non-Hispanic) and the following race categories:

- Caucasian
- Black or African American
- Asian
- Native Hawaiian or Other Pacific Islander
- American Indian or Alaska Native
- Other

In addition, the primary endpoint will be summarized by treatment group and site, and by underlying disease.

8.8 Interim Analysis

An unblinded interim analysis was performed for testing of the primary hypotheses. A detailed Interim Analysis Plan had been provided in a separate document (Interim analysis Plan Version 1.0, February 14, 2019).

152 randomized patients were included in the interim analysis. Interim results will not be disclosed before final database close and unblinding.

8.9 Data Monitoring

In this trial, an independent Data Safety Monitoring Board (DSMB) was involved to monitor patient safety.

The working principles were defined in a DSMB charter describing the composition of the DSMB, responsibilities, organization, flow of information, evaluation and decision principles, and interactions.

8.10 Analysis of the Primary Endpoint

The primary study variable is the number of patients in each treatment group with conjugated bilirubin levels > 2 mg/dL during the first 28 days of study treatment, confirmed by a second sample collected 7 days after the first sample.

Statistical Analysis Plan

FK Study Identifier: SMOF-018-CP3

Number and incidence of patients with conjugated bilirubin levels > 2 mg/dL during the first 28 days of study treatment will be presented overall and stratified by the patients' underlying disease (No NEC / NEC) for each stage of the study and the combined stages. Differences between treatment groups will be quantified using the estimates of the common relative risk (Mantel-Haenszel estimate) - controlling for stratum - and the Cochran-Mantel-Haenszel statistics of general association for the combined strata, and corresponding 95% confidence intervals will be presented.

Data from each stage without imputation will be summarized with descriptive statistics, combined data from both stages with and without imputation will be summarized with descriptive statistics using the ITT analysis set and the per protocol set.

8.11 Analysis of Secondary Efficacy Variables

The secondary outcome parameters for efficacy will be summarized descriptively for the ITT analysis set and the per protocol set from both stages combined.

8.11.1 Age-Standardized Growth – Body Weight, Length, and Head Circumference

Growth and development of infants will be evaluated based on the parameters body weight, body length/height, and head circumference. Data will be age-standardized using growth charts as suggested by Fenton (Fenton et al., 2013) and the World Health Organization (WHO) Multicenter Growth Reference Study (MGRS; WHO 2006, 2007). Term infants (i.e., born at ≥ 37 completed weeks of gestational age) will be evaluated solely using WHO charts. For preterm infants, growth data collected at ≤ 50 weeks of completed gestational age will be standardized with Fenton charts. Otherwise, WHO charts will be applied.

Fenton charts at 50 weeks gestational age are equivalent to the WHO standard at 10 weeks chronological age. Thus, a preterm infant with growth data as of > 50 weeks of gestational age needs to be evaluated along the x-axis of the WHO charts at gestational age subtracted by 40 weeks.

Standardization according to the WHO standard will be derived for all growth parameters using the SAS macros provided by WHO (WHO, Anthropometry version 3.2.2, 2011).

The authors of the Fenton charts published various Z-score and percentile calculators for download. Age-standardized Z-scores of the standard normal distribution will be derived using a publicly available Microsoft Excel calculation tool (Actual Age Calculator v7, 2015).

Z-scores will be assigned to any of the three categories: normal, low for age, high for age. The following cut-off values for categorization will be used (Wang & Chen, 2011; WHO Child Growth Standards, 2006):

Version (of CSP): 3.0

CONFIDENTIAL

page 36 of 56

date: 5 OCT 2020

Annex No.: **[REDACTED]**
Document No.: **[REDACTED]**

00

1

Date:

Page:

[REDACTED]
36 of 56

Statistical Analysis Plan

FK Study Identifier: SMOF-018-CP3

Categorization of Z-Scores on Fenton and WHO Growth Charts

Z-score cut-off	Category	Corresponding p%-percentile
$Z \leq -1.88$	Low for age	$p \leq 3\%$
$-1.88 < z < 1.88$	Normal	$3\% < p < 97\%$
$Z \geq 1.88$	High for age	$p \geq 97\%$

Categorization of age-standardized Z-score will be performed for the end of the initial treatment phase and the end of the extended treatment phase. The number and percentage of patients with low, normal and high weight for age will be presented by time point (including end of treatment and end of study) and treatment group.

Anthropometric data will be listed and summarized by time point and treatment group, and Spaghetti plots and box plots over time will be displayed by treatment group.

Patient listings of measured anthropometric data (body weight [g], height/length [cm], head circumference [cm], corresponding Z-scores after standardization for age, and allocated categories will be provided.

